8.6.3. Laboratory Evaluations

Selected laboratory data (using conventional units) will be summarized using only observed data. Data and change from baseline at all scheduled time points will be summarized.

Selected laboratory data (using conventional units) will be summarized by the observed data and by the change from baseline across time.

Graded laboratory abnormalities will be defined using the grading scheme defined in [Appendix 4](#). Grading of laboratory abnormalities for analysis purposes will be performed by the central laboratory.

Incidence of treatment-emergent laboratory abnormalities, defined as values that increase at least one toxicity grade from baseline at any time post baseline, will be summarized by monitoring group. If baseline data are missing, then any graded abnormality (i.e., at least a Grade 1) will be considered treatment-emergent.

Laboratory abnormalities that occur before the first dose of Tenofovir DF or after the last dose of Tenofovir DF plus 30 days will be included in a data listing.

8.6.4. Other Safety Evaluations: Analyses of BMD

Cumulative incidence of at least a 4% decrease from baseline in BMD (spine BMD and whole body BMD) using time-to-event methodology will be summarized and compared between treatment groups using 95% confidence intervals for difference in person time rates.

The percent change from baseline in BMD (spine BMD and whole body BMD) will be summarized over time and compared between treatment groups using the Generalized Linear Model. Lumbar spine and whole body z-scores (derived from DEXA-derived BMD assessments) and the changes in z-scores from Baseline will be summarized.

BMD (via DEXA scan) and serum bone biochemical markers will be summarized over time. Changes from study baseline in bone biochemical markers will also be summarized after adjusting for potential confounders such as age and gender..

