Baseline measures for Groups 1 and 2 will include laboratory assessments for HBV DNA, HBV serology, HCV, HDV, and HIV polymerase chain reaction (PCR) testing, HBV genotyping, serum renal and bone chemistries, liver function, hematology, urinalysis. Dual Energy X-ray Absorptiometry (DEXA) imaging and a physical exam, including current concomitant medications (including dietary supplements) and any renal or bone AEs, will also be collected.

FREQUENCY OF STUDY PROCEDURES ([Appendix 2](#)):

Subjects enrolled to either Group 1 or 2 will have the following measures assessed:

- HBV DNA: every 12 weeks from Baseline to Week 96
- HBV serology: every 24 weeks from Baseline to Week 96
- Liver chemistry (i.e., alanine aminotransferase (ALT), alkaline phosphatase (ALP), aspartate aminotransferase (AST), total and direct bilirubin, total protein, albumin, gamma glutamyl transpeptidase (GGT), lactate dehydrogenase (LDH), creatine kinase (CK): every 24 weeks from Baseline to Week 96
- Hematology (i.e., complete blood count with differential and platelets, PT/INR): every 24 weeks from Baseline to Week 96
- Physical Examination and Drug Dispensing: every 12 weeks from Baseline to Week 96

Subjects enrolled to Group 1 will have the following additional monitoring:

- DEXA: every 24 weeks from Baseline to Week 96 (5 scans)
- Serum bone chemistry (i.e., calcium, phosphorus, vitamin D levels (25-hydroxy and 1,25 dihydroxyvitamin), parathyroid hormone (PTH), osteocalcin, bone-specific alkaline phosphatase, N and C telopeptides): every 24 weeks from Baseline to Week 96
- Serum renal chemistry (i.e., glucose, creatinine, calculated creatinine clearance, magnesium, bicarbonate, chloride, potassium, sodium): at 4 weeks and 12 weeks from Baseline and every 12 weeks thereafter to Week 96, according to SmPC

- Urinalysis (i.e., protein, glucose, creatinine, phosphate, bicarbonate, blood, calcium): at 4 weeks and 12 weeks from Baseline and every 12 weeks thereafter to Week 96

Subjects enrolled to Group 2 will have the following monitoring:

- DEXA: every 48 weeks from Baseline to Week 96 (3 scans)
- Serum bone chemistry (i.e., calcium, phosphorus, vitamin D levels (25-hydroxy and 1,25 dihydroxyvitamin), PTH, osteocalcin, bone-specific alkaline phosphatase, N and C telopeptides): every 48 weeks from Baseline to Week 96
- Serum renal chemistry and urinalysis according local standards of care

Product, Dose, and
Mode of
Administration:

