8.6. Safety Analysis

All safety data collected on or after the date that Tenofovir DF was first dispensed up to the date of last dose of Tenofovir DF will be summarized by monitoring group. Data for any pre-treatment and treatment-free follow up periods will be included in data listings.

The primary safety analysis will be performed after the last assigned subject reaches Week 96. The analysis will evaluate the difference between renal or bone AEs recorded within each of the monitoring groups with respect to the primary safety endpoint, estimating the cumulative incidence proportions using time-to-event methodology and performing comparisons using 95% confidence intervals for differences in proportions.

The proportion of subjects in each monitoring group with renal or bone AE leading to permanent discontinuation of Tenofovir DF through Week 96 will be summarized. Descriptive statistics such as n, mean, standard deviation, median, Q1, Q3, minimum and maximum) by monitoring group will be used to report demographics and time to event summaries, and a Wilcoxon rank sum test may be used to compare AEs between monitoring groups.

For categorical safety data including incidence of AEs and categorizations of laboratory data, a Fisher's exact test will be used to compare monitoring groups. For continuous safety data including laboratory data, a Wilcoxon Rank sum test will be used to compare monitoring groups. Subgroup analyses of safety endpoints will include analyses by assigned monitoring group, age groups, and geographical location of study site.

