1.2. Study Design

Design Configuration and Subject Population
	
This study is a post-authorization, randomized open-label study comprised of adolescents who initiate 245mg PO once daily tTDF therapy for the treatment of HBV in clinical sites across Europe. The subjects will be assigned in a 1:1 ratio to one of two monitoring groups using a validated computer-generated tool for randomization. Subjects will be assigned to Group 1 or 2 upon enrollment into the study but prior to Baseline laboratory and DXA imaging assessments.

Treatment Groups
	
Monitoring Group 1 will receive tTDF 245mg PO once daily for the treatment of CHB infection, followed over 96 weeks using an enhanced monitoring protocol which includes more frequent laboratory bone biomarker testing and lumbar spine and whole-body DXA scans (Baseline, and Weeks 24, 48, 72, 96) than that which is specified for Group 2. With the exception of an enhanced monitoring protocol for bone and renal outcomes, subjects will be managed according to local standards of care.
 
Monitoring Group 2 will be the comparator group of subjects receiving tTDF 245mg PO once daily for the treatment of CHB infection, and with the exception of pre-specified bone monitoring, will be managed according to local standards of care. Group 2 will receive serum bone biomarker testing, and lumbar spine and whole body DXA at Baseline, Weeks 48 and 96.

Key Eligibility Criteria
	
Inclusion Criteria
 
 • Subjects must meet all inclusion criteria as stated in the protocol to be eligible for participation in this study. These include: 
 — 12 to <16 years of age — Documented chronic HBV infection (e.g. positive serum HBsAg\geq 6 months) — Weight \geq 35 kg — Able to swallow oral tablets — Negative serum β-HCG pregnancy test — Estimated glomerular filtration rate (creatinine clearance) \geq 80 mL/min/1.73m²

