1.4. Sample Size and Power

Planned Sample Size	100 subjects (50 subjects to one of two monitoring groups)
Power Statement	
The study employed two monitoring protocols which specified the same laboratory and imaging tests for bone and renal markers and differed in the frequency of testing. Group 1 receives more frequent monitoring which is protocol-defined or SmPC specified, and Group 2 subjects are monitored according to a less frequent DXA schedule for BMD and followed the local standard of care for renal monitoring. It is hypothesized (H_0) that there would have been no difference in the timing, management, or subject outcomes resulting from renal or bone AEs among the two monitoring regimens. With a one-tailed test of $\alpha=0.05$, and assuming a non-inferiority margin of 0.10, the study had at least 80% power to detect a difference between the monitoring regimens beyond the specified margin of non-inferiority.
 
The primary safety endpoint is cumulative incidence of at least a 4% decrease from study baseline (BL) in spine bone mineral density (BMD) through Week 96.
 
The null hypothesis is the difference (Group 1 – Group 2) is equal to 0.
 
The alternative hypothesis is the difference (Group 1 – Group 2) is not equal to 0.

Actual Enrollment and Impact on Power	
The study failed to achieve its targeted enrollment of 100 patients, 50 per monitoring group. The study was discontinued as a result of the recent approval of Tenofovir alafenamide fumarate (TAF) medicine which offers a safer treatment option for CHB patients and due to low subject enrollment after the CHMPs assessment of the 18 month interim enrollment report. At the time of its closure the study enrolled 30 patients, 15 per monitoring group. The total enrolled subjects are underpowered to statistically detect differences in outcomes between monitoring groups.

--	--

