7.3. Bone Mineral Density and Bone Biochemical Markers

BMD primary endpoints to be evaluated include:

- Cumulative incidence of at least a 4% decrease from baseline in spine BMD
- Spine BMD (g/cm^2) and change from baseline
- Percent change from baseline in spine BMD (categorical)
- Z-Scores for spine BMD (g/cm^2) and change from baseline (categorical)
- Cumulative incidence of at least a 4% decrease from baseline in whole-body BMD
- Whole-body BMD (g/cm^2) and change from baseline
- Percent change from Baseline in whole-body BMD (categorical)
- Z-Scores for whole-body BMD (g/cm^2) and change from baseline (Categorical)

Cumulative incidence of at least a 4% decrease from BL in spine and whole-body BMD will be summarized by monitoring group and study week for each randomization age group (12-14 years, 15-17 years). No inferential statistics will be computed.

The percent change from BL in spine BMD and in whole-body BMD will also be summarized categorically by monitoring group and overall for each study week using the following categories: ≤ -4 , > -4 to ≤ -2 , > -2 to ≤ 0 , > 0 to ≤ 2 , > 2 to ≤ 4 , > 4 , and Missing. No inferential statistics will be computed.

Z-score and changes from BL in z-score will also be summarized categorically (n, mean, standard deviation, median, Q1, Q3, minimum and maximum) by monitoring group and overall for each study week. No inferential statistics will be computed.

Spine BMD and whole-body BMD clinical status will also be summarized categorically by monitoring group and overall for each study week using the following categories: > -1 , -1 to -2 , < -2 , Total, and Missing. No inferential statistics will be computed.

Serum bone biochemical markers will be summarized (n, mean, standard deviation, median, Q1, Q3, minimum and maximum) by monitoring group and overall for each study week, as well as the changes from BL. In all cases of serum bone biochemical markers, no inferential statistics will be computed.

The following bone biochemical markers as previously mentioned in the laboratory results section will be assessed:

- N-telopeptide (nmol BCE/L)
- C-telopeptide (ng/mL)
- Serum osteocalcin (ng/mL)

- Bone-specific alkaline phosphatase ($\mu\text{g/L}$)
- Serum PTH (pg/mL)
- Vitamin D (25-hydroxy, [ng/mL])

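### The by-group incidence of a BMD decrease of at least 4% rests on four scheduled post-baseline scans in Group 1 and two in Group 2, so it tilts against Group 1 unless every loss persists to the next shared scan

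*Protocol*

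**What the plan says.** The two groups take the same drug and differ in monitoring. The Protocol synopsis gives Group 1 "DEXA: every 24 weeks from Baseline to Week 96 (5 scans", baseline included, and Group 2 "DEXA: every 48 weeks from Baseline to Week 96 (3 scans", baseline included. SAP 1.2 repeats the schedules.

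Protocol 8.6 describes the primary safety analysis as "estimating the cumulative incidence proportions using time-to-event methodology and performing comparisons using 95% confidence intervals for differences in proportions". Protocol 8.6.4 applies this to the BMD threshold: the incidence of a decrease of at least 4% is estimated "using time-to-event methodology will be summarized and compared between treatment groups using 95% confidence intervals for difference in person time rates".

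SAP 1.4 names as primary safety endpoint the "cumulative incidence of at least a 4% decrease from study baseline (BL) in spine bone mineral density (BMD) through Week 96" and adds: "The null hypothesis is the difference (Group 1 – Group 2) is equal to 0". SAP 7.3 states: "Cumulative incidence of at least a 4% decrease from BL in spine and whole-body BMD will be summarized by monitoring group and study week", with no inferential statistics. The tables are 26.1 (spine) and 27.1 (whole body).

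Neither document limits the by-group incidence to scans that both groups have, uses an interval-censored method, or asks for a second scan. SAP 7.2.2.3 defines confirmation for laboratory results; SAP 7.3 has no counterpart for BMD. SAP 3.8.3 says a time-to-event analysis need not use one value per window, and SAP 7.8 declares no change to the safety analysis.

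**The concern.** An any-crossing endpoint grows with the number of looks. Group 1's scheduled scans (Weeks 24, 48, 72, 96) contain all of Group 2's (Weeks 48, 96). With equal true loss and complete follow-up, Group 1's expected incidence therefore cannot be lower. It is higher whenever a crossing at Week 24 or 72 is no longer seen at the next shared scan, whether through scan error or recovery. Recovery is not far-fetched: Protocol 1.2.3.1 reports paediatric HIV subjects in Study 926 whose BMD decreases had partly or fully resolved by Week 96, although two of them had stopped the drug.

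At stake is the meaning of a Group 1 excess. Protocol 3.2 asks whether enhanced monitoring helps to prevent bone and renal harm. An excess that comes from extra scans could be read as a worse bone outcome in the more closely watched group. With 15 subjects per group, one extra detected case is 1/15 = 6.7 points, and the tables carry no warning that scan counts differ.

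**Working it through.** **1. The plan's own figures.** Scans: 96/24 + 1 = 5 and 96/48 + 1 = 3, as stated, so 4 and 2 post-baseline. Reference rate: Protocol 8.9 gives 5.8% (1.2-15.9%) at 72 weeks. With the 52 treated subjects of Protocol 1.2.3.1, 3/52 = 5.8%, exact interval 1.2-15.9%; this reproduces.

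**2. Assumption.** The 5.8% is cumulative over the prior trial's three post-baseline scans (Weeks 24, 48, 72).

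**3. Independent scans (bound), complete follow-up.**
- Per scan: q = 1 - (1 - 0.058)^(1/3) = 0.0197.
- Group 1: 1 - (1 - q)^4 = 7.66%. Group 2: 1 - (1 - q)^2 = 3.91%. Difference 3.75, or 3.8 points.
- Rates per 100 person-years. Group 1: 0.0766 / [(24/52) × (1 + (1-q) + (1-q)² + (1-q)³)] = 4.27. Group 2: 0.0391 / [(48/52) × (1 + (1-q))] = 2.14.

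**4. All losses persist, complete follow-up.** Both groups 7.7%. The Group 2 rate is 0.0766 / [(48/52) × (1 + (1-q)²)] = 4.23, against 4.27. The gap is about 0. If half of crossings persist to the next scan, simulation gives about 7.7% vs 5.7%.

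**5. Scan error with a shared baseline scan.** Simulation of 300,000 subjects: individual linear slopes, mean gain 0-3% per year, scan SD 1, 1.5 or 2%, slope SD set so that the Week 24/48/72 incidence is 5.8%. Cells where noise alone exceeds 5.8% are excluded (8 of 12 usable).

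| Scan SD | Group 1 minus Group 2 |
|---|---|
| 1% | 0.5 to 1.3 points |
| 1.5% | 1.5 to 2.6 points |
| 2% (one usable cell) | 3.3 points |

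Across cells, Group 1 is 6.5-10.6% and Group 2 is 3.2-9.4%. At the ends of the 1.2-15.9% band the gap is 0.2-0.8 and 0.5-5.7 points. Counting Weeks 48 and 96 only, the gap is at most 0.15 points (simulation error about 0.1).

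**6. Early exit, losses persisting.** Assumptions: exits spread evenly over 96 weeks; hazard -ln(0.942)/72 per week; F(t) is the probability of a loss by week t. On exit, the next visit's assessments are done. By successive 12-week exit interval the last scan is:
- Group 1: none, exit, 24, exit, 48, exit, 72, exit. Mean of F = (0 + 1.48 + 1.97 + 3.42 + 3.91 + 5.33 + 5.80 + 7.20)/8 = 3.64%.
- Group 2: none (three times), exit, 48 (three times), exit. Mean of F = (3.42 + 3 × 3.91 + 7.20)/8 = 2.79%.
- Per 15 subjects: 0.55 vs 0.42 expected events.
- Scanned subjects only (divide by 7 and 5 instead of 8): 4.2% vs 4.5%. The Group 1 excess is gone.

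A separate simulation with 20% leaving per 12 weeks and persisting losses gives crude 3.6% vs 2.8%, rates 4.2 vs 3.2 per 100 person-years, and Kaplan-Meier at Week 96 equal to within simulation error (about 7.6% vs 7.5%).

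**7. The early-exit scan has two readings.** Protocol 6.4.2 to 6.4.6 each say that a subject who stops before the visit completes that visit's assessments. Read visit by visit, as in step 6, a stop shortly before Week 24 or 72 brings a DEXA in Group 1 only. Read literally, every early stop is also before Week 96 and brings a DEXA in both groups. With persisting losses the literal reading makes the groups equal. With independent crossings, expected events per 15 are 0.6 vs 0.2 (visit by visit) or 0.7 vs 0.4 (literal).

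**The case against.** **Much of the remedy is already planned.** SAP 7.3 also tabulates percent change in BMD by group and study week, with categories for '≤ -4' and 'Missing' (Tables 26.2 and 27.2). The Week 48 and Week 96 rows already give the shared-scan counts. This stands. What is missing is a count cumulated over the two windows and any guidance that it, and not Table 26.1 or 27.1, is the fair contrast.

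**Differential detection is part of the question.** The hypothesis in Protocol 8.9 concerns timing, management and outcomes under two regimens, and Protocol 3.2 names early detection. This stands in part: the all-scan incidence is the natural detection measure and should be kept. But SAP 1.4 also makes it the primary safety endpoint with a null of no group difference, so it is not only a detection measure.

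**Primary is ambiguous.** Protocol 2 and 8.1.1 and SAP 1.1 name percent change in BMD as primary. Agreed, and that comparison at Weeks 48 and 96 is not affected.

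**The practical effect is small.** An excess of 0.5-3.3 points on 15 subjects is 0.08-0.5 of a subject. SAP 1.4 and 2.1 already say that the study cannot establish group differences. This stands for the final analysis.

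**A shared-window contrast is not fully clean.** It conditions on being scanned after randomization. Protocol 7.5.6 sets different handling of bone abnormalities by group, so a Week 24 finding could affect later BMD or exit in Group 1 only. This stands as a limit.

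**A reader might infer that early exit always inflates Group 1.** The documents do not support that. Protocol 8.6 and 8.6.4 call for time-to-event methods, and Kaplan-Meier with exit unrelated to BMD is not biased by exit alone. SAP 7.3 states no denominator beyond the analysis set, and among scanned subjects the direction reverses when losses persist.

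**Conclusion.** The point holds. The plan compares, and displays by group, an any-crossing incidence with twice as many scheduled post-baseline looks in Group 1, without a shared-scan or confirmation rule. That much comes directly from the documents.

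The size does not. At the 5.8% reference rate it runs from about 0 (all losses persist, complete follow-up), through roughly 0.5-3.3 points (assumed scan SD 1-2% and mean gain 0-3% per year), to an independent-scan bound of 3.8 points. Early exit adds to it only for crude proportions over the Safety Analysis Set and for person-time rates, and the amount depends on which early-exit DEXA reading was used.

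Two stronger readings should be resisted. First, the final analysis is not exposed to a false positive test: SAP 7.3 computes none for this endpoint, and with 15 per group and two completers in all, the harm is to interpretation. Second, no effect on power can be claimed, because Protocol 8.9 names neither the endpoint nor the direction for its 0.10 margin. The rule matters most for the Protocol 8.6 and 8.6.4 comparison as written. It should be fixed.

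**What to change.** Add to SAP 7.3, log in SAP 7.8, and apply as the rule for the Protocol 8.6 and 8.6.4 comparison:

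- **Contrast.** The Group 1 versus Group 2 contrast in BMD decreases of at least 4% uses only scans in the Week 48 (Days 253-420) and Week 96 (Days 589-756) windows of SAP Table 3-2, in both groups. It cumulates, per subject, the '≤ -4' results behind Tables 26.2 and 27.2. Numbers scanned and missing are shown per group and window. Any person-time rate uses the same scans.
- **Detection measure.** The all-scan incidence by group stays in Tables 26.1 and 27.1, footnoted: Group 1 has twice the scheduled post-baseline scans, and a difference is not by itself evidence of a worse bone outcome.
- **No event lost.** Report the number of Group 1 subjects whose crossing was seen only on a Week 24, Week 72 or exit scan.
- **Exit scans.** State which reading of the early-exit DEXA rule was applied.

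Cost: wording and table shells, no new data. Downside: the contrast is conditional on a scan in a shared window. With evenly spread exits (assumption), 252/672 = 37.5% of non-completers, about 5 of 14 per group, leave before Day 253 and drop out of it. Only 84/672 = 12.5% reach the Week 96 window, so the contrast rests mainly on Week 48. If a Week 24 crossing leads to exit, that event leaves the contrast (at most about 15 × 0.0197 = 0.3 of a subject at the assumed per-scan risk), which is why the all-scan incidence and the extra count are kept.

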Study Title: Pharmacoepidemiology study to define the long-term safety profile of tenofovir disoproxil fumarate (Tenofovir DF, Viread®) and describe the management of Tenofovir DF-associated renal and bone toxicity in Chronic Hepatitis B (CHB)-infected adolescents aged 12 to <18 years in Europe

IND Number: This is a non-IND study

EudraCT Number: 2014-004939-39

Clinical Trials.gov Identifier: Not Available

Study Centers Planned: Approximately 25 centers in Europe.

Objectives: The primary objective of this study is as follows:

- To characterize the long term (i.e., 96 weeks of follow up) bone safety profile of open-label Tenofovir DF treatment in CHB-infected adolescents. This includes prospectively evaluating and comparing the bone mineral density (BMD) change between CHB- infected adolescents 12 to < 18 years of age treated with Tenofovir DF in European treatment centers who are assigned to one of two schedules for renal and bone laboratory monitoring and BMD measurement. Primary study outcome will be the percent changes in BMD from Baseline through study Week 96.

The secondary objectives of this study are as follows:

- To document all serious adverse drug reactions (SADR) and all renal- and bone-related adverse events (AEs), including renal and bone laboratory abnormalities
- To determine the time to diagnosis of renal and bone AEs and document the resulting patient management and outcome(s)
- To assess the clinical management and outcomes of renal- and bone-related \geq Grade 3 laboratory markers and clinical SAEs

- To assess the efficacy and tolerability of Tenofovir DF in adolescents with CHB infection
- To assess the use of oral vitamin D, calcium and phosphate supplementation and explore the association between supplement use and rates of bone and renal AEs
- To describe the demographics and disease characteristics of adolescents with CHB infection treated with Tenofovir DF.
- To describe reasons for discontinuation of Tenofovir DF.

Study Design:

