For this study design and limited age groupings, matching at enrollment on other factors such as demographics, would likely have a marginal benefit on the strength of the results; matching may occur (e.g., age, gender, ethnicity, duration of Tenofovir DF exposure) during the analysis phase as specified in the statistical analysis plan (SAP).

The strengths of the study include a focus on long term outcomes related to renal and bone adverse event reporting in a vulnerable population. Use of two real world cohorts will permit the evaluation of whether a schedule of more frequent clinical assessments of adolescent patients on Tenofovir DF benefit from early detection of potential AEs. Previous studies across multiple HIV and HBV infected patient populations have demonstrated a modest risk for both bone and renal AEs related to Tenofovir DF-containing medications. Understanding whether changes in monitoring frequency for serum and urine biomarkers and use of more frequent DEXA may provide early detection to subtle changes in bone or renal dynamics and be beneficial in enhancing patient outcomes.

The feasibility of study design implementation has been assessed using clinical trials data from GS-US-174-0115. Demographic, adverse event reporting, clinical and laboratory markers, and DEXA screen results at baseline and at regular intervals from clinical trials show a range of 90-100% reporting adherence for key variables, when applicable.

The primary safety analysis will be conducted after the last assigned subject reaches Week 96 of Tenofovir DF treatment.

Subjects with the following characteristics will be eligible for enrollment: 12 to <16 years of age with chronic HBeAg-positive or HBeAg-negative HBV infection (e.g., HBsAg-positive for at least 6 months)

Subjects must be naïve to Tenofovir DF, but could have received prior treatment with other anti-HBV nucleoside/nucleotide therapy or interferon (e.g., treatment failure). Previous treatment with interferon should have ended at least six months prior to the Screening Visit.

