8.1.2. Primary Endpoint

The primary endpoint of this study is:

- The identification of bone AEs occurring in subjects taking Tenofovir DF between Baseline and Week 96 of treatment, including the identification of $\geq 4\%$ percent reduction in BMD within subjects and between monitoring groups from Baseline.

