1.3. End of Study

The end of study is defined as the completion of TDF therapy and close-out monitoring by the last enrolled subject (e.g., last enrolled subject completes 96 Weeks of treatment and monitoring).

Randomization
	
Approximately 100 TDF-naïve patients were planned to be randomized in a 1:1 ratio to receive treatment with TDF and assigned to one of two monitoring groups (50 in each group was planned). The subjects were assigned to one of two monitoring groups using a validated computer-generated tool for randomization (dynamic block assignment by site to ensure there are at least 4 subjects randomized per site). Subjects were assigned to Group 1 or 2 upon enrollment into the study but prior to Baseline laboratory and DXA imaging assessments.
 
The study population was enrolled through one of 23 participating European clinics across several countries (eg., Bulgaria, Poland, Romania, Italy, France, Spain, and the United Kingdom) commencing June 2015

-----------------------------	---

Site and/or Stratum Enrollment Limits	There were no enrollment limits imposed at the sites.
Study Duration	
Subjects will be treated with TDF for 96 weeks. The planned duration in-study for a given subject is at least 2 years. TDF is currently approved for use in patients across all specified study countries with participating study clinics aged 12 years of age and up.
 
Subjects who permanently discontinue TDF will be asked to return for an end-of-treatment visit within 72 hours of the last dose of TDF. Subjects who permanently discontinue TDF will be followed for 24 weeks off treatment or up to initiation of active treatment, whichever occurs first.

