7.8. Changes From Protocol-Specified Safety Analyses

No alterations to the protocol-specified safety analysis have been made. The study has been canceled due to low enrolment and due to the approval of TAF for HBV in adolescents in November 2016 as a safer treatment option for patients. With two subjects completing 96 weeks of treatment the safety analysis will shift to focus on subjects' available treatment exposure to TDF.

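### Protocol 8.6.4 compares percent change in BMD between groups with a model that names no covariates, and the SAP adds none, although baseline BMD, age and sex are collected

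*Protocol*

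**What the plan says.** The protocol synopsis states: "Primary study outcome will be the percent changes in BMD from Baseline through study Week 96". Protocol 2 and 8.1.1 and SAP 1.1 say the same in their objectives, and include a comparison of BMD change between the monitoring groups. Protocol 8.1.2 (like 3.1) differs. It gives the primary endpoint as "The identification of bone AEs occurring in subjects taking Tenofovir DF between Baseline and Week 96 of treatment, including the identification of" a fall of at least 4% in BMD.

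The between-group analysis of percent change is a single sentence in Protocol 8.6.4: spine and whole-body values "will be summarized over time and compared between treatment groups using the Generalized Linear Model". It gives no covariate, link, time point or repeated-measures structure. The next paragraph of that section treats a different set of measurements more fully: "Changes from study baseline in bone biochemical markers will also be summarized after adjusting for potential confounders such as age and gender".

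Protocol 3.2 leaves the door open for later: "matching may occur (e.g., age, gender, ethnicity, duration of Tenofovir DF exposure) during the analysis phase as specified in the statistical analysis plan (SAP"). The SAP does not take this up. SAP 3.3 says only that randomisation was not stratified by age or region.

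SAP 7.3 summarises percent change in BMD in categories and computes no inferential statistics for it. SAP 2.1 makes the final analysis descriptive, because only two subjects completed 96 weeks. SAP 7.8 nevertheless states: "No alterations to the protocol-specified safety analysis have been made".

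**The concern.** In subjects aged 12 to under 16 at entry, BMD change depends on growth. Protocol 1.2.3.1 calls a rise in mean spine BMD expected in adolescents, and SAP 7.3 splits the 4% endpoint by age group. Baseline BMD, age and sex are the obvious markers of where a subject stands in growth. Dividing by the baseline value does not in itself make percent change independent of baseline.

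Leaving the covariates open has two consequences. Variance that these covariates could explain stays in the error of the group difference. The choice of model is also left until the data are in hand, for an outcome that the objectives call primary. Randomisation keeps the unadjusted contrast unbiased on average. With no stratification by age and small groups, though, a chance imbalance in age or sex can still move the observed BMD difference, including in descriptive by-group tables.

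**Working it through.** **Inputs from the documents.** Planned size is 50 per group (Protocol 8.9). Actual enrolment is 15 per group (SAP 1.4) through 23 clinics (SAP 1), with two Week 96 completers (SAP 2.1). Both groups are scanned at Baseline and Weeks 48 and 96; the Week 24 and 72 scans are Group 1 only (Protocol Appendix 2). Baseline BMD, age and sex are collected (Protocol 8.4).

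**Not in the documents.** There is no SD for percent change in BMD and no R-squared of that change on baseline BMD, age and sex. I assume an R-squared from 0 to 0.5 and work in SD units.

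**Is there a plan figure to reproduce?** Not for this outcome. The 80% power in Protocol 8.9 concerns renal or bone AE outcomes with a margin of 0.10, so it cannot serve as the starting point here.

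**Step 1: gain.** The ratio of adjusted to unadjusted standard error is √(1 − R²).

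**Step 2: cost.** Estimating q = 3 covariates inflates the variance by about 1 + q/(N − q − 3):
- N = 100: √(1 + 3/94) = 1.016
- N = 30: √(1 + 3/24) = 1.061

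**Step 3: translation.** At 50 per group, with a conventional two-sided 0.05 and 80% power (my choice, since the plan gives none for this outcome), the detectable difference is (1.960 + 0.842) × √(2/50) × √(1 − R²) SD. This column leaves out the Step 2 cost.

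| Assumed R² | SE ratio | SE ratio with cost, N = 100 | SE ratio with cost, N = 30 | Detectable difference, 50 per group (SD) |
|---|---|---|---|---|
| 0 | 1.000 | 1.016 | 1.061 | 0.560 |
| 0.1 | 0.949 | 0.964 | 1.006 | 0.532 |
| 0.3 | 0.837 | 0.850 | 0.887 | 0.469 |
| 0.5 | 0.707 | 0.718 | 0.750 | 0.396 |

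**Step 4: break-even.** Setting (1 − R²)(1 + q/(N − q − 3)) = 1 gives R² = q/(N − 3):
- N = 100: 3/97 = 0.03
- N = 30: 3/27 = 0.11

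The SAP does not say how many of the 30 have a Week 48 scan. If it were 20, as an illustration, break-even would be 3/17 = 0.18.

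**Step 5: site.** SAP 1.3 describes "dynamic block assignment by site to ensure there are at least 4 subjects randomized per site", so a site term might be expected. With fixed site effects, group and three covariates, the residual degrees of freedom are:
- 100 subjects in the planned 25 or so centres: 100 − 25 − 1 − 3 = 71
- 30 subjects in 23 clinics: 30 − 23 − 1 − 3 = 3, against 30 − 2 − 3 = 25 without site

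**The case against.** The strongest reply is that the final analysis as planned loses nothing. SAP 7.3 fits no BMD model, SAP 2.1 explains why the analysis is descriptive, and SAP 1.4 says that the study is underpowered. That stands. The gain belongs to the protocol's planned comparison, or to a Week 48 estimate if one is kept.

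Growth is also partly handled elsewhere. Protocol 8.6.4 and SAP 7.3 summarise BMD Z-scores, Protocol 8.6 plans safety subgroups by age group and site location, and SAP 7.3 reports the 4% endpoint by age group. That is fair, but none of these gives an adjusted between-group difference in percent change.

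A reader might draw four stronger conclusions, which the documents do not support:
- **That the model is set to adjust for nothing.** The protocol is silent on covariates, and Section 3.2 contemplates later matching on age and gender. Silence is not a rule.
- **That adjustment would lift the stated 80% power, for instance to 89%.** That 80% concerns AE outcomes, not BMD change.
- **That the gain can be read from the SD of Z-score change in Protocol 1.2.3.1.** Z-scores are already referenced to age, so that SD does not describe percent change or what these covariates would explain of it.
- **That blocking by site calls for a site term.** No gain from site is shown, and at 30 subjects in 23 clinics the term is close to unusable.

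SAP 7.8 also deserves a full reading. After denying any alteration, it says that the focus shifts to available exposure. It still does not say that the Generalized Linear Model was dropped, and SAP 7.3 keeps a Wilcoxon comparison of bone markers to Week 48.

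**Conclusion.** The concern holds as a minor, inexpensive gap in pre-specification. The protocol's model for percent change in BMD names no covariates, the SAP does not supply them, and three sensible ones are already collected. At the planned 50 per group, the standard error would fall by about 5%, 16% or 29% for an R-squared of 0.1, 0.3 or 0.5, before the cost of estimating the covariates. With 30 subjects the benefit is uncertain: an R-squared of 0.1 gives none, while 0.3 still gives about 11% after that cost.

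These figures depend wholly on the assumed R-squared. Calling percent change the primary outcome follows the objectives; the endpoint sections say otherwise. A reader might infer that precision is being wasted in the reported final analysis, but no between-group BMD model is planned there. What does need correcting in the SAP is that the protocol's comparison was removed without being recorded as a change.

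**What to change.** In Protocol 8.6.4, state the model for percent change in spine and whole-body BMD: terms for monitoring group, baseline BMD, age and sex, at the scans shared by both groups (Weeks 48 and 96), reporting the adjusted group difference with a 95% CI. Keep the percent-change scale.

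For the 30 subjects enrolled, choose one of two routes in the SAP:
- report the adjusted difference at Week 48 as an estimate with its 95% CI, without a p-value and without a site term, giving the number scanned in each group; or
- state in SAP 7.8 that the protocol's between-group BMD model was dropped, and why.

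The cost is a few lines of model wording and one table, or one sentence in SAP 7.8. No new data are needed. The downside is the estimation of three covariates, which can slightly widen the interval if they predict BMD change weakly.
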